10.6.4.4. Laboratory Parameters

Laboratory Parameters

 • If a laboratory value which is expected to have a numeric value for summary purposes, has a non-detectable level reported in the database, where the numeric value is missing, but typically a character value starting with '<x' or '>x' (or indicated as less than x or greater than x in the comment field) is present, the number of significant digits in the observed values will be used to determine how much to add or subtract in order to impute the corresponding numeric value. 
 ○ Example 1: 2 Significant Digits = '< x ' becomes $x - 0.01$

CONFIDENTIAL

201410

Laboratory Parameters

 ○ Example 2: 1 Significant Digit = '> x' becomes $x + 0.1$ ○ Example 3: 0 Significant Digits = '< x' becomes $x - 1$

 ● If there is more than one laboratory value on the same date for the same laboratory test, then the laboratory values associated with scheduled visits will be used. Hgb summaries and analyses are an exception and should use the data handling conventions outlined in Section 10.6.3.

 ● For purposes of flagging worst-case post baseline laboratory values: 
 ○ If there are multiple scheduled values on the same day, or only multiple unscheduled values on the same day, then the average of the values on that day should be used for the purpose of determining the worst-case value.

 ● The following will be used to convert laboratory values from SI units to conventional units [Iverson, 2007]: 
 ● MCHC and Albumin: Divide the g/L value by 10 to get the g/dL value. ● Albumin corrected calcium: Divide the mmol/L value by 0.25 to get the mg/dL value. ● Creatinine: Divide the umol/L value by 88.4 to get the mg/dL value. ● eGFR: Multiply the mL/sec/1.73m² value by 60 to get the mL/min/1.73m² value. ● Phosphate: Divide the mmol/L value by 0.323 to get the mg/dL value. ● BUN: Divide the mmol/L value by 0.357 to get the mg/dL value ● Total cholesterol, LDL-C and HDL-C: Divide the mmol/L value by 0.0259 to get the mg/dL value. ● Vitamin B9: Divide the nmol/L by 2.266 to get the ng/mL value
Normal Range Categories, PCI Criteria Categories and Worst Case Values

 ● Normal range categories are: To Low, To Normal or No Change, To High ● PCI criteria categories are: To Low, To w/in Range or No Change, To High ● Subjects with a missing baseline value are to be assumed to have a normal/within range baseline value. ● The determination of the worst case post baseline value takes into account both planned and unscheduled assessments. ● Worst case can be either High or Low. 
 ○ If a subject has both a decrease 'To Low' and an increase 'To High', then the subject is counted in both the 'To Low' and 'To High' categories. ○ If a subject was High at baseline and decreases to Low during the time interval, then the subject is counted in the 'To Low' category. Likewise, if a subject was low at baseline and increases to high during the time interval, then the subject is counted in the 'To High' category. ○ Subjects are only counted in the 'To Normal or No Change' or 'To w/in Range or No Change' category if their values are: 
 ▪ When using normal ranges: Normal at baseline and have no high and no low values; When using PCI ranges: Within range at baseline and have no high and no low values ▪ High at baseline and do not change to low ▪ Low at baseline and do not change to high

10.6.4.5. Vital Signs

Vital Signs
Pre- and Post- Dialysis HR & Weight

 For subjects undergoing dialysis in-clinic, both pre- and post- dialysis HR & weight values will be measured. Unless otherwise specified, for summaries of HR & weight values, the post-dialysis HR & weight values for subjects undergoing dialysis in-clinic will be used.

 If there is more than one vital sign value on the same date for the same vital sign value, then the vital sign values associated with scheduled visits will be used. If there are multiple values from a scheduled visit on the same date, then the average of the scheduled values will be used.

 For purposes of flagging worst-case post baseline vital sign values: 
 If there are multiple scheduled values on the same day, or only multiple unscheduled values on the same day, then the average of the values on that day should be used for the purpose of determining the worst-case value.

10.6.4.6. COVID-19

COVID-19
Exposure Duration

 For subjects who DO NOT experience the event, the exposure duration is calculated as: (last non-zero dose date or end date of time block, whichever occurs sooner – treatment start date or start date of time block, whichever occurs later + 1)/365.25 For subjects who DO experience the event, the exposure duration is calculated as: (start date of AE – treatment start date or start date of time block, whichever occurs later + 1)/365.25
Exposure Adjusted Incidence Rate

 Exposure adjusted incidence rate (rate/100 PY) = (number of subjects with the adverse event during the time block / total exposure duration across all subjects) * 100
Time Periods

 Pre COVID-19 pandemic period: the date of interest is prior to the country specific start date of COVID-19 pandemic measures. For example, for recruitment and demographic summaries, the subject will be counted in the pre COVID-19 period, if the randomization date of the subject is prior to the country specific start date of COVID-19 pandemic measures. During COVID-19 period: the date of interest is after the country specific start date of COVID-19 pandemic measures. For example, for recruitment and demographic summaries, the subject will be counted in the during COVID-19 period, if the randomization date of the subject is after the country specific start date of COVID-19 pandemic measures. There is currently no post COVID-19 period.

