8.2.8. Other Safety Analyses

Medical Conditions

A listing of all medical conditions for all subjects will be provided by treatment group. Each subject's corresponding medical condition(s) will be provided using the medical history free text.

COVID-19 Analyses

The following COVID-19 related displays will be provided.

A summary of the number and percentage of subjects for the following assessments will be produced: Case Diagnosis, COVID-19 Test performed, and Results of the COVID-19 test.

A summary of exposure adjusted incidence rates over time (see Section 10.6.4) will be produced by treatment group for any treatment emergent AE, any treatment emergent SAE, and any treatment emergent Severe AE, for two periods – pre COVID-19 pandemic and during COVID-19 pandemic. The summary will be produced overall, by Country, Region, Sex, and by Age at randomization (Grouping 2) (see Section 10.10.1). A summary of exposure adjusted incidence rates by treatment group will also be produced for Common (>5%) AEs for two periods – pre COVID-19 pandemic and during COVID-19 pandemic.

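### The COVID-19 exposure formula has no zero floor and no at-risk restriction, so subjects not treated in a block can subtract person-time from its adverse event rates

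*SAP*

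**What the plan says.** SAP 8.2.8 (COVID-19 Analyses) plans exposure-adjusted incidence rates by treatment group "for two periods – pre COVID-19 pandemic and during COVID-19 pandemic". They cover any treatment-emergent AE, SAE and severe AE, overall and by country, region, sex and age. A further table covers the common AEs.

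SAP 10.6.4.6 gives the derivation:

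- **Subject without the event.** Exposure ends at "last non-zero dose date or end date of time block, whichever occurs sooner". From this is subtracted "treatment start date or start date of time block, whichever occurs later + 1" (the one day is added to the difference). The result is divided by 365.25.
- **Subject with the event.** The AE start date replaces the end point; the start point is the same.
- **Rate.** Subjects with the AE in the block, divided by "total exposure duration across all subjects", times 100.
- **Periods.** A date is pre-pandemic when "the date of interest is prior to the country specific start date of COVID-19 pandemic measures" and during-pandemic when it falls after that date. No third period is defined: "There is currently no post COVID-19 period".

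Neither section restricts the sum to subjects treated in the block or sets a negative difference to zero.

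**The concern.** Earlier end minus later start plus one is the usual length of overlap between two intervals. It is valid only when they overlap. When they do not, it returns minus the number of days lying between them. Treatment was planned for 52 weeks, and the blocks are set by calendar date, so some subjects will probably have no treated time in one of the blocks. Summed as written, each of them takes person-time away from subjects who were treated in that block.

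These tables are meant to show whether AE rates changed once pandemic measures began. A denominator that is too small inflates the rate, by different amounts in the two blocks, so an apparent change could come from the formula alone.

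**Working it through.** The SAP states no exposure total or rate for these tables, so there is no figure to reproduce. The check applies the formula as written.

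**1. Single subjects.** Assume measures start on 15 March 2020 (the documents give no date). Read literally, the pre block ends on 14 March and the during block starts on 16 March. No subject here has the event.

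| Treated | Pre block, as written | During block, as written | Correct |
|---|---|---|---|
| 1 Jun 2018 to 30 May 2019 | 363 + 1 = 364 days (0.997 y) | −291 + 1 = −290 days (−0.794 y) | 0.997 and 0 |
| 1 Jun 2020 to 15 Dec 2020 | −79 + 1 = −78 days (−0.214 y) | 197 + 1 = 198 days (0.542 y) | 0 and 0.542 |
| 1 Oct 2019 to 28 Sep 2020 | 165 + 1 = 166 days (0.454 y) | 196 + 1 = 197 days (0.539 y) | as written |

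The third subject was treated for 364 days, but the blocks hold 166 + 197 = 363. The missing day is the country start date, which is neither before nor after itself.

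**2. Subjects with the event.** The second formula does not say that the event must fall in the block. An AE starting on 1 November 2019 gives −136 + 1 = −135 days in the during block. On the same loose reading, an AE starting after the pre block ends would carry pre-block time past that end, an error in the other direction. Restricting the formula to in-block events removes both.

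**3. A total that can be checked by hand.** Assume 300 subjects (the planned number), 12 months' treatment each, even enrolment over 24 months, and no events.

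- *Enrolment ends at the block start.* Stop dates run from −12 to +12 months around it. The mean is 0, so the sum as written is 0. The positive part averages (12²/2)/24 = 3 months, so true exposure is 300 × 3/12 = 75 patient-years.
- *Enrolment ends 6 months earlier.* Stop dates run from −18 to +6 months. The mean is −6 months, giving 300 × (−6/12) = −150 patient-years. The positive part averages (6²/2)/24 = 0.75 months, or 18.75 patient-years.

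**4. A range of calendars.** Assume 300 subjects, uniform enrolment over 1.5 to 3 years, 364 days of treatment, 30% stopping uniformly before Week 28 (the early-stopping figure in Protocol 9.2.1), and measures starting 1 to 3.5 years after first randomization. All subjects use the no-event formula. That simplification is mild for an uncommon AE but not for any AE. Over 18 calendars:

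| | Subjects negative | Total as written (patient-years) | Total floored at 0 |
|---|---|---|---|
| During block | 7% to 88% | +183 to −367 | 8.5 to 192 |
| Pre block | 0% to 67% | +225 to −158 | 42 to 225 |

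A moderate case is enrolment over 2 years with measures at 1.5 years. The pre block is 102.4 against 121.1, so the rate is inflated by 121.1/102.4 = 1.18. The during block is 64.3 against 112.5, inflated by 112.5/64.3 = 1.75. With equal true rates, the during-to-pre ratio would read 1.75/1.18 = 1.48.

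**5. Are such subjects likely?** The COVID supportive plot in SAP 7.1.2.5 starts about a year after first randomization and marks the start of measures with a reference line. This suggests that measures came later than that, when the earliest subjects were at or past 52 weeks and early stoppers were already off treatment. For the pre block, the documents do not show whether anyone started treatment after measures began.

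**The case against.** The fair defence is that the text uses the standard overlap formula under the label of exposure duration and limits the numerator to events in the block. A sensible programmer would read the denominator as subjects exposed in the block and drop the rest. No number in the SAP is wrong, only a condition left unstated.

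Part of this stands. The formula is correct for every event-free subject treated in the block, and the programming may well turn out right. But the text sums over all subjects, and the in-block condition is attached to the numerator only. The period rule classifies a single date, with randomization date as its example; it does not truncate an interval. Where the SAP wants a zero rule it writes one: SAP 10.6.3.2 sets IV iron records outside the window to zero duration. No such rule appears here.

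A reader might infer that the rates will be negative or worthless. The documents do not support that. Of the 18 calendars above, the during total is negative in 9 and the pre total in 4, while in 8 the pre block has no error at all. These are counts of assumed scenarios, not probabilities.

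A reader might also infer that the error biases one arm against the other. That would need the calendar timing of treatment to differ by arm, and nothing in the documents shows that it does.

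**Conclusion.** The point holds: as written, the derivation gives the wrong denominator whenever a subject's treatment does not overlap the block. For event-free subjects the error always runs towards a smaller denominator and a higher rate. The single-subject results depend only on the dates chosen. The totals rest on assumed enrolment and pandemic calendars and on treating everyone as event-free, so they show that the error can be large, not how large it is. The by-country and other subgroup tables are more exposed than the overall one, because a group that enrolled early can have a negative total while the overall total stays positive.

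The reach is small. These are descriptive summaries. The main AE incidence rates use a separate person-time definition (SAP 10.6.4.3) with no calendar blocks, and the primary and principal secondary analyses are untouched. The boundary-date gap costs one day per subject on treatment that day and is trivial, but it is as easily closed.

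**What to change.** Revise SAP 10.6.4.6 so that, for each block, the sum runs only over subjects with at least one on-treatment day in it:

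- **No event with onset in the block:** [min(last non-zero dose date, block end) − max(treatment start, block start) + 1] / 365.25.
- **Event with onset in the block:** [first in-block AE start − max(treatment start, block start) + 1] / 365.25.
- **Numerator:** only AEs with onset in the block.
- **Boundary:** assign the country start date to one block, for example during, and state each block's first and last day.

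Keep both formulas. Flooring the first at zero and applying it to everyone would count time after the event for subjects who had one. State also that a subject whose only event came before the block is treated as event-free in it, if that is intended.

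The cost is a few lines of SAP text and a small programming change. No new data are needed.

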10.6.5. Patient Reported Outcomes

SF-36
General Information & Scoring

 The SF-36 acute version 2 is a 36-item generic quality of life instrument designed to measure a subject's level of performance in the following eight health domains: Physical Functioning, Role-Physical (role limitations caused by physical problems), Social Functioning, Bodily Pain, Mental Health, Role-Emotional (role limitations caused by emotional problems), Vitality, and General Perception of Health. Scoring of the questionnaire data will be performed using Optum PRO CoRE scoring software version 1.4 using a norms-based scoring approach using 2009 norms and the maximum data recovery mode to handle missing data. The 8 domain scores and scores for the physical and mental component summary measures will be provided by the Optum PRO CoRE software.
EQ-5D-5L
General

 The EQ-5D-5L is a self-assessment questionnaire, consisting of five items covering five dimensions (mobility, self care, usual activities, pain/discomfort, and anxiety/depression). Each dimension is measured by a five-point Likert scale (no problems, slight problems, moderate problems, severe problems, and extreme problems). The responses for the five dimensions together form a five-figure description of a health state (i.e., the score of 11112 describes the health state of no problems with mobility, self-care, usual activities or pain/discomfort, but slight problems with anxiety/depression). Each of these five-figure health states has an attached valuation (index value), expressed as a single index on a scale from 0-1, where 1 is [REDACTED] and 0 is [REDACTED]. EQ-5D-5L health states are converted to a single summary index score by applying a country-specific value set formula that essentially attaches weights to each of the levels in each dimension. The EuroQol Group's United Kingdom (UK) value set for the health states will be used for all subjects, regardless of country.
EQ-VAS
General

 The EQ-VAS is a self-assessment visual analogue scale, ranging from 0=[REDACTED] – 100=[REDACTED].
PGI-S
General

 The PGI-S is a 1-item questionnaire designed to assess a subject's impression of disease severity on a 5-point disease severity scale (absent, mild, moderate, severe, or very severe). Scores range from [REDACTED] as follows: 
 [REDACTED] [REDACTED] [REDACTED]

CONFIDENTIAL

201410

PGI-S	
General	
	
 ○ CCI ○ [REDACTED]

PGI-C	
General	
	
 • The PGI-C is a 1-item questionnaire designed to assess a subject's impression of change in their anemia of CKD on a 7-point Likert-type response scale (very much improved, moderately improved, minimally improved, no change, minimally worse, moderately worse, or very much worse). • Scores range from [REDACTED] to [REDACTED] as follows: 
 ○ CCI ○ [REDACTED] ○ [REDACTED] ○ [REDACTED] ○ [REDACTED] ○ [REDACTED] ○ [REDACTED]

CKD-AQ	
General	
	
 • The CKD-AQ is a newly-developed 21-item PRO measure assessing symptoms and symptom impact in patients with anemia associated with CKD. An interim cut of blinded observations from approximately 400 participants, approximately 350 from study 200808 (GSK Document Number 2015N230102_03) and approximately 50 from study 201410 (GSK Document Number. 2015N234534_01), who had completed the baseline (Day 1) CKD-AQ was taken to establish the scoring algorithm and any potential domains of the instrument. Further details of the scoring can be found in the psychometric report (GSK Document Number). • CKD-AQ originally had 23 questions/items, the psychometric analysis identified three domains (multi-item scales) and four single items, which consist of 21 items. The three domains are: (1) a Tired/Low Energy/Weak scale consisting of ten items – Items CCI CCI - This section contained Clinical Outcome Assessment data collection questionnaires or indices, which are protected by third party copyright laws and therefore have been excluded. [REDACTED]; (2) a Chest Pain/Shortness of Breath scale consisting of four items – Items CCI CCI CCI This factor was labeled Chest Pain/Shortness of Breath.); and (3) a Cognitive scale consisting of three item – Items CCI CCI The four CKD-AQ single items are: Items CCI

CONFIDENTIAL

201410

CKD-AQ
General

CCI CCI [REDACTED], were retained based upon their CKD-relevant content. The CKD-AQ domains and single-item measures were recoded based on a 0-100 scoring with 0 representing CCI [REDACTED] and 100 CCI [REDACTED].
 
 • Scoring instruction: 
 ○ Step 1: For items 1-8, 17-23, recode from 5-pt scale (CCI [REDACTED] CCI [REDACTED]) to 0-100 (CCI [REDACTED] scale by using $(5\text{-row score}) * 25$; for items 9-16, recode from 11-pt scale (CCI [REDACTED]) to 0-100 scale (CCI [REDACTED]) by using $(10\text{-raw score}) * 10$. ○ Step 2: calculate the domain and single item scores as follows: (items 16 and 23 were NOT used currently based on the psychometric report.) 
 ▪ Tired/Low Energy/Weak domain: average items CCI [REDACTED] (0-100 scale) ▪ Chest Pain/Shortness of Breath domain: average items CCI [REDACTED] (0-100 scale) ▪ Cognitive domain: average items CCI [REDACTED] (0-100 scale) ▪ CCI [REDACTED] (0-100 scale) ▪ CCI [REDACTED] (0-100 scale) ▪ CCI [REDACTED] (0-100 scale) ▪ CCI [REDACTED] (0-100 scale)

10.7. Appendix 7: Premature Withdrawals & Handling of Missing Data

10.7.1. Premature Withdrawals

Element	Reporting Detail
General	
 • Subject study completion (i.e. as specified in the protocol) was defined as completing all phases of the study through the End of Treatment visit (i.e. Week 52), with the following exception: subjects who die while on study are also considered as having completed the study. • Withdrawn subjects will not be replaced in the study. • All available data from subjects who were withdrawn from the study will be listed and all available planned data will be included in summary tables and figures, unless otherwise specified. • Per protocol, subjects may prematurely discontinue study drug but are encouraged to remain in the study.

10.7.2. Handling of Missing Data

Element	Reporting Detail
General	
 • Missing data occurs when any requested data is not provided, leading to blank fields on the collection instrument : 
 ○ These data will be indicated by the use of a “blank” in subject listing displays, unless all data for a specific visit are missing in which case the data is excluded from the table. ○ Answers such as “Not applicable” and “Not evaluable” are not considered to be missing data and should be displayed as such.
Outliers	
 • Any subjects excluded from the summaries and/or statistical analyses will be documented along with the reason for exclusion in the clinical study report.

10.7.2.1. Handling of Missing and Partial Dates

Element	Reporting Detail
General	Partial dates will be displayed as captured in subject listing displays.
Concomitant Medications	
 • Partial dates for any concomitant medications recorded in the CRF will be imputed using the following convention: 
 ○ If the partial date is a start date, a '01' will be used for the day and 'Jan' will be used for the month ○ If the partial date is a stop date, a '28/29/30/31' will be used for the day (dependent on the month and year) and 'Dec' will be used for the month. • The recorded partial date will be displayed in listings.
Adverse Events	
 • The eCRF allows for the possibility of partial dates (i.e., only month and year or only year) to be recorded for AE start/worsening and end dates. In such a case, the following conventions will be applied for calculating the time to onset and the duration of the event: 
 • Imputing a Start/Worsening Date from a Partial Start/Worsening Date:

CONFIDENTIAL

201410

Element	Reporting Detail
	
 ○ If an imputed worsening date is before the start date, then the start date will be used as the imputed worsening date. ○ Completely missing stop date: 
 ➤ If only the day is missing, the first of the month will be used unless the Screen Week -2 visit date or treatment start date also occurs in the same month. 
 ● If the treatment start date occurs in the same month, then the treatment start date will be used as the start/worsening date. ● Otherwise, if the Screen Week -2 visit date occurs in the same month, then the Screen Week -2 visit date will be used as the start/worsening date. ➤ If the day and month are missing, then '01' will be used for the day and 'Jan' will be used for the month unless the Screen Week -2 visit date or treatment start date also occurs in the same year. 
 ● If the treatment start date occurs in the same year, then the treatment start date will be used as the start/worsening date. ● Otherwise, if the Screen Week -2 visit date occurs in the same year, then the Screen Week -2 visit date will be used as the start/worsening date. ○ Partial or non-missing stop date is before treatment start date: 
 ➤ If only the day is missing, then the first of the month will be used unless the Screen Week -2 Visit date also occurs in the same month; in this case the Screen Week -2 Visit date will be used as the start/worsening date. ➤ If the day and month are missing, then '01' will be used for the day and 'Jan' will be used for the month unless the Screen Week -2 Visit date also occurs in the same year; in this case the Screen Week -2 Visit date will be used as the start/worsening date. ○ Stop date is partial with the same year (or year and month) as the treatment start date or is on or after the treatment start date: 
 ➤ If only the day is missing, then the first of the month will be used unless the start date of study treatment also occurs in the same month; in this case the study treatment start date will be used as the start/worsening date. ➤ If the day and month are missing, then '01' will be used for the day and 'Jan' will be used for the month unless the start date of study treatment occurs in the same year; in this case the study treatment start date will be used as the start/worsening date. ● Imputing a Stop Date from a Partial Stop Date: 
 ○ Latest of (start date and latest worsening date) is on or before the treatment stop date or is partial with the same year (or year and month) as the treatment stop date:

CONFIDENTIAL

201410

Element	Reporting Detail
	
 ➤ If only the day is missing, the last day of the month will be used unless the treatment stop date also occurs in the same month; in this case the treatment stop date will be used as the stop date. ➤ If the day and month are missing, then '31' will be used for the day and 'Dec' will be used for the month, unless the stop date of study treatment also occurs in the same year; in this case the study treatment stop date will be used as the stop date. ○ Latest of (start date and latest worsening date) is partial or non-missing and is after treatment stop date: 
 ➤ If only the day is missing, the last day of the month will be used unless the study conclusion date also occurs in the same month; in this case, the study conclusion date will be used as the stop date. ➤ If the day and month are missing, then '31' will be used for the day and 'Dec' will be used for the month, unless the study conclusion date also occurs in the same year; in this case, the study conclusion date will be used as the stop date. ● Completely missing start or end dates (i.e. no year specified) will remain missing, with no imputation applied. Consequently, time to onset and duration of such events will be missing.
CV Safety Endpoint Events	Discussed in Section 10.6.4

CONFIDENTIAL

201410

